#### 1. Background

In the past century, measures have been increasingly implemented in the field of anesthesia to combat the incidence of preoperative and perioperative complications. One such measure has been the development and subsequent modifications to airway management via the difficult airway algorithm (1). Difficulty with the airway management is a primary concern as an inability to oxygenate the patient can result in irreversible injury to vital organs and ultimately death (2).

Difficulties encountered with mask ventilation and intubation result in a significant portion of complications and mortality encountered during anesthesia (3). Among all patients undergoing general anesthesia, the rate of difficult intubation ranges from 0.5% to 10% depending on the exact definition (4). In addition, analysis conducted using closed claims spanning over 3 decades found that difficulties in airway management account for 6% of all claims during general anesthesia (5). The inability to perform effective mask ventilation or tracheal intubation can be due to a multitude of patient related factors. These factors include increasing age, increasing weight, history of snoring, lack of teeth, Mallampati class, limited mouth opening, protruding tongue, and beard presence (6). Establishing new airway management techniques and assessing which techniques lead to better outcomes (both efficiency and effectiveness) are necessary to reduce anesthesia-related morbidity and mortality. In the event that intubation proves to be difficult or impossible, mask ventilation is often used as a rescue technique to provide oxygenation and ventilation to a patient until the patient's airway can be successfully intubated. Therefore, clinicians should be made aware of the most effective techniques regarding difficult airway management and effective ventilation strategies.

On arrival to the operating room, the large majority of patients are ventilating and oxygenating without any airway adjuncts for assistance. Therefore, the inability to perform effective mask ventilation after induction of anesthesia likely occurs due to technical failure to generate positive ventilation and/or upper airway obstruction. When considering all causes of failure for adequate ventilation, it is often challenging to precisely determine the cause of failed mask ventilation. Failure of mask ventilation often occurs due to leaks around the mask from an inadequate seal, tongue and/or epiglottis obstructing the upper airway, laryngospasm, or aspiration. However, airway obstruction from redundant tissue likely accounts for the majority of failure. Understanding the underlying physiology of a difficult airway enables clinicians to proficiently manage a difficult airway.

4

In an effort to reduce morbidity and mortality associated with difficult airway management, adjustments to technique and innovations of ventilation have been studied extensively in patients with difficult airways. Recently, it was demonstrated that the approach to two-hand mask ventilation techniques had varying levels of success as measured by tidal volumes and rate of ventilator failure depending on the hand-grip used by the person attempting ventilation. (7). In addition to exploring the effect of hand grips on mask's ventilation success, further innovations in ventilation have been searched including the use of tracheal tube in pharynx (TTIP) ventilation. Ventilation using the TTIP technique is effective and can be used as a bridging technique for oxygenation **(this technique is illustrated in Figure 1)**. An endotracheal tube can be inserted via the nostril or oral cavity, and subsequently advanced until the tip of the tube reaches approximately the level of the glottis. By ventilation within seconds after failed mask ventilation in all 4 difficult airway cases encountered in a study by Kristensen in 2005 (7). Unfortunately, there is a lack of well-designed and executed randomized trials to validate its efficacy in a true or potential difficult airway.

Moreover, this technique seems easy to learn, conceptualize, and use in any urgent or emergency difficult airway management situation. Potential advantages of TTIP technique are multiple and include: 1) bypasses the mask seal, 2) does not require successful laryngoscopy and tracheal intubation, 3) flexible laryngoscopy or surgical airway can be concurrently performed when the patient is ventilated or at least oxygenated, and more importantly, 4) it does not require the correct insertion of a conventional supraglottic airway (SGA), like a laryngeal mask airway (LMA). As long as the tip of the endotracheal tube reaches the level of the glottis, the positive pressure of ventilation should be enough to open a collapsed upper airway. Two scenarios that may render this technique ineffective are laryngospasm and massive aspiration. If laryngospasm is present as the potential cause, adequate muscle paralysis should be effective in correcting this obstruction. In massive aspiration, clearance of the debris should help with ventilation. Finally, the potential inadequate seal is a concern with this technique. Since the cuff is not placed in the lumen of the trachea and is not inflated, the seal must be achieved via the lips. The seal can be established with one or two hands as shown in Figures 2 and 3, respectively. Even if a complete seal is not achieved, holding the lips around the tube can create a seal sufficient for positive pressure ventilation.

5

[figure not shown]

Figure 1. Illustration of endotracheal tube in pharynx technique.

[figure not shown]

Figure 2. Tracheal tube in pharynx and seal at lips with one hand

Figure 3. Tracheal tube in pharynx and seal at lips with two hands

While improvements in intubation technologies have been of primary focus, there has been relatively little consideration into comparing the effectiveness of traditional mask ventilation vs. TTIP. In other words, how do we optimize and improve the difficult airway protocol for use during urgent or emergent circumstances? Furthermore, little is known on the specific order that the two ventilation modalities are used during a difficult airway situation. The maintained consistency of order in the standard airway protocol can be attributed to the success the difficult airway algorithm has had in decreasing complications (6). However, rates of CICV (cannot intubate, cannot ventilate) have not seen a reduction despite new innovations (8). It is possible that alterations to the order of the current difficult airway procedure could lead to significant improvement of difficult airway management.

#### 2. Hypothesis

TTIP ventilation is more effective than mask ventilation in patients with a potentially difficult airway

[figure not shown]
#### 3. Specific aims

- 3.1 To determine the efficacy of TTIP-first ventilation
- 3.2 To compare the efficacy of TTIP first ventilation with the current practice of mask-first ventilation

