#### 5. Outcomes

- 5.1 Primary outcome: The success rate of ventilation with TTIP vs. mask, defined as at least one of the first three breaths shows three phases of expired CO2 profile.
- 5.2 Secondary outcomes:
- 5.2.1 Expired tidal volume of ventilation with TTIP vs mask.
- 5.2.2 Peak inspiratory airway pressure achieved with TTIP vs. mask ventilation

5.2.3 Dynamic airway resistance is defined as the peak inspiratory flow divided by the corresponding airway pressure.

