#### 7. Data acquisition and analysis

All ventilatory settings and measured parameters displayed on the operating room ventilator (Datex Ohmeda AS/5, Helsinki, Finland), including expired tidal volume (VTeVTe), flow waveforms, end-tidal carbon dioxide partial pressure, exhaled carbon dioxide waveforms, and vital signs displayed on the monitor will be preserved electronically intra-operatively and video recorded from the time of pre-oxygenation and 5 minutes after intubation. The target number for ventilation is 10 breaths for both TTIP and mask ventilation techniques. Only the last five breaths (only three breaths for failed ventilation) will be used for final analysis to calculate the VTe and PIP. The mean of five breaths (three breaths if mask ventilation failed) is used as a single data point. Study team members converting the video recorded data to digital data will be blind to the interventions and the sequence of interventions. Once the study is completed and the digital data is collected, the study team members will be unblinded.

The primary analysis is to perform the McNemar test on the paired outcomes of all subjects. In addition to the McNemar test, we will find odds ratio estimate of failure for TTIP versus mask ventilation, together with its 95% confidence interval (CI), by stratifying on subject to handle dependence. Further, we will find the estimate of failure rate difference and its 95% Wald CI. We will consider and evaluation the covariance when estimating the standard error of failure rate difference.

We will perform multivariable analysis by using GEE method to estimate adjusted odds ratio of failure for TTIP versus mask ventilation. We will let the GEE model to include an odds ratio to accommodate within-subject association. The regression equation of the GEE model will include treatment (TTIP, mask ventilation), period (1, 2) and treatment-by-period interaction. The last two factors facilitates different carry-over effects for these two ventilation methods. If all factors will be significant, we will report the odds ratios of failure for TTIP versus mask ventilation at periods 1 and 2 separately. P values less than 0.05 will be considered as significant. All statistical analyses will be performed by using the SAS software (version 9.4, the SAS Institute, Cary, NC).

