#### 8. Predicted outcome and its significance

[figure not shown]
The study team assumes that TTIP-first ventilation (A) will be superior to mask first ventilation (B) as shown by a 50% reduction of failed ventilation. Additionally, we predict a significant improvement in the measured parameters (expired tidal volume, flow waveforms, exhaled carbon dioxide waveforms) with TTIP compared to that with mask ventilation. The study team hopes that TTIP will be an effective rescue technique for failed mask ventilation. Such a finding will provide evidence of the efficacy of TTIP and TTIP can be used as an alternative for rescuing failed mask ventilation and/or tracheal intubation. Its implication can be in the perioperative setting, emergency department, and pre-hospital resuscitation. We expect the implication of TTIP would improve the difficult airway management and therefore outcome.

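### Aim 3.2 and Section 8 compare TTIP-first with mask-first, but the plan's only first-technique comparison of the randomised groups is reported conditionally and has no stated power

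*Combined protocol and SAP*

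**What the plan says.** Two questions run through the document.

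**Order.** Section 1 (Background) closes with "It is possible that alterations to the order of the current difficult airway procedure could lead to significant improvement of difficult airway management". Aim 3.1 is "To determine the efficacy of TTIP-first ventilation" and Aim 3.2 is "To compare the efficacy of TTIP first ventilation with the current practice of mask-first ventilation". Section 8 names the groups: "TTIP-first ventilation (A) will be superior to mask first ventilation (B) as shown by a 50% reduction of failed ventilation". In Section 6, A and B are the randomised sequences, TTIP then mask and mask then TTIP.

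**Technique.** The hypothesis in Section 2 is "TTIP ventilation is more effective than mask ventilation in patients with a potentially difficult airway". The primary outcome in Section 5 is "The success rate of ventilation with TTIP vs. mask, defined as at least one of the first three breaths" with a three-phase expired CO2 profile. Section 7 states: "The primary analysis is to perform the McNemar test on the paired outcomes of all subjects". It adds an odds ratio stratified on subject and a failure-rate difference, both within subject. Section 9 gives 99.4% power for a two-sided McNemar test in 200 subjects, with 250 enrolled.

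Period enters only through the GEE model in Section 7, which has treatment, period and their interaction. Section 7 says the last two terms are there to allow for carry-over. Separate odds ratios for periods 1 and 2 are to be reported only when all factors are significant.

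**The concern.** McNemar counts the subjects who failed with mask alone and with TTIP alone. Exchanging the sequence labels leaves the statistic unchanged, so it carries no information on which order is better. Half of its TTIP data (Group B) come from TTIP used second, and half of its mask data (Group A) from mask used second. In each case the second technique follows either a full minute or three failed breaths of the other.

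The comparison that matches Aim 3.2 is Step 1 failure in Group A against Step 1 failure in Group B. It is randomised and free of carry-over from the other technique. The plan contains it, as the period-1 odds ratio, but behind a significance condition and without a power statement. The risk is twofold. The estimate for a stated aim may never be published, and a significant McNemar result may be read through Section 8 as showing that TTIP-first is superior to mask-first.

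**Working it through.** **Inputs (Section 9).** Mask failure 34%; TTIP failure at most 20%, taken as 20%; discordant proportion 25%; two-sided 5%; 200 evaluable, 250 enrolled, allocated 1:1. This gives 100 per group evaluable, or 125 if nobody drops out. Section 8 gives a 50% reduction without a base rate. I assume 34%, so 34% v 17%.

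**1. The plan's own power.** McNemar power = Φ[(d√n − 1.96√pd) / √(pd − d²)], with d = 0.14, pd = 0.25, n = 200:
(1.980 − 0.980) / 0.480 = 2.083, so power is 98.1%. Exact enumeration also gives 98.1%. The stated 99.4% is slightly high but agrees within 2 points. It describes the paired technique test.

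**2. Step 1, Group A v Group B.** Power = Φ[(d√n − 1.96√(2p̄(1−p̄))) / √(p₁(1−p₁)+p₂(1−p₂))], n per group.

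- 34% v 20%, n = 100: (1.400 − 1.96×0.628) / 0.620 = 0.273, power 60.8%
- 34% v 17%, n = 100: (1.700 − 1.96×0.616) / 0.605 = 0.814, power 79.2%
- n = 125: 70.5% and 87.4% respectively

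At 34% v 20% the 95% CI half-width is 1.96×0.620/√n: 12.2 points with 100 per group and 10.9 with 125.

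**3. How often the period-1 odds ratio would be reported.** Write T1 and M2 for the failure logits of Group A at Steps 1 and 2, and M1 and T2 for those of Group B. The period-1 log odds ratio is T1 − M1, which is Group A v Group B on first technique. The interaction is (T1 − M1) − (T2 − M2) = (T1 + M2) − (M1 + T2), a contrast of the two sequences summed over both steps.

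With no period or carry-over effect, the period and interaction terms are each significant about 5% of the time. Under effect coding, if they were independent, both would be significant in about 0.05 × 0.05 = 0.25% of trials. Simulation of the saturated model with paired covariance (100 per sequence, 20,000 runs) gives 0.3% for all three factors under effect coding and about 1% under reference coding. Section 7 does not state the coding. If one assumes that carry-over lowers mask failure after TTIP to 25%, the figure is 1% to 10%.

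**4. A constructed illustration, not a forecast.** Let Group A fail 30% with TTIP first and 34% with mask second. Let Group B fail 34% with mask first and 10% with TTIP second. The pooled rates are 34% for mask and (30 + 10)/2 = 20% for TTIP, exactly the planned 14 points. The Step 1 difference is only 34 − 30 = 4 points (95% CI half-width 12.9 with 100 per group). McNemar cannot distinguish this from a trial in which TTIP fails 20% in both positions.

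**The case against.** The strongest reply is that the order question does have an analysis. The GEE model is fitted whatever McNemar shows, its period-1 odds ratio is exactly Group A against Group B on the first technique, and its interaction is a sequence contrast. That stands. A reader might infer that the plan has no order analysis at all, and the text does not support this. What remains is that Section 7 assigns the period and interaction terms to carry-over, that the interaction sums both steps and so is not the first-technique comparison, and that the period-1 estimate is withheld unless all factors are significant.

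A reader might also infer that both aims are comparative, or that the plan claims 99.4% power for Aim 3.2. Neither is so. Aim 3.1 asks only for the efficacy of TTIP-first, and Section 9 ties the 99.4% to McNemar.

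The hypothesis, primary outcome, primary analysis and sample size all agree on technique, so the order wording may be the outlier. Section 1 and Section 8 also speak of TTIP against mask, and Section 8 of TTIP as a rescue, that is, used second. This is a fair reading and is why rewording is an acceptable remedy. Still, Section 8 names A and B, which goes beyond loose wording.

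The 30%/10% pattern has no basis in the documents. In that scenario the reporting condition would be met in anything from 0.3% to over 60% of trials, depending on coding, so the plan might detect it. Finally, without order effects the Step 1 contrast estimates the same marginal difference as the paired data, less precisely. That is correct, but McNemar cannot show that order effects are absent.

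**Conclusion.** The concern holds in a limited form. Aim 3.2 and the Section 8 prediction have only a conditional analysis with no stated power. If the trial behaves as planned, with no order effect, the estimate that answers Aim 3.2 would be reported in about 0.3% to 1% of trials. The Step 1 comparison has about 61% power at 34% v 20% and about 79% at 34% v 17% with 100 per group, or about 71% and 87% with 125.

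These figures rest on Section 9's rates, on 20% being the TTIP rate and not just its ceiling, and on 34% being the base for Section 8's 50%. The McNemar test remains valid for the Section 2 hypothesis. The point concerns what may be concluded about order.

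**What to change.** In Section 7, name the Step 1 failure comparison of Group A with Group B as the analysis for Aim 3.2. Report it as a risk difference with 95% CI together with the period-1 odds ratio, whatever the significance of the GEE terms. Report Group A's Step 1 failure rate for Aim 3.1. Keep McNemar as the primary test of the Section 2 hypothesis.

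In Section 8, state that superiority of TTIP-first over mask-first will be concluded only from the Group A v Group B comparison. Alternatively, if only technique was meant, reword Aim 3.2 and Section 8 as TTIP versus mask.

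In Section 9, state that the 99.4% applies to the paired technique test, and give the Step 1 power alongside it. Use one set of group labels: Section 6 has A and B, while Section 9 has 1 and 2 in the opposite order.

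The cost is a few sentences and one two-group comparison on data already being collected. The small downside is that the order claim will be less precise than the technique claim.

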#### 4. Patient enrollment

This study will be carried out in the main operative rooms at Memorial Hermann Hospital in the Texas Medical Center (TMC). The study team will approach the patients in the respective preoperative holding area after reviewing their medical records to determine eligibility. Once the study team believes that a particular patient is eligible to participate in the study, the study team will provide that patient with detailed information about the study and obtain informed consent from the patient.

- 4.1. Inclusion criteria:
  - I. 18 or older years of age
  - II. BMI > 30 kg/m^2

- III. Mallampati class III or IV
- IV. Requiring general anesthesia

#### 4.2. Exclusion criteria:

- I. Acute and chronic respiratory disorders, including COPD and asthma
- II. ASA physical status classification  $\geq$ IV
- III. Emergency surgery
- IV. Induction requiring rapid sequence for intubation
- V. Patients requiring awake intubation
- VI. Pregnant women
- VII. Untreated ischemic heart disease
- VIII. Contraindication for mask ventilation

#### 5. Outcomes

- 5.1 Primary outcome: The success rate of ventilation with TTIP vs. mask, defined as at least one of the first three breaths shows three phases of expired CO2 profile.
- 5.2 Secondary outcomes:
- 5.2.1 Expired tidal volume of ventilation with TTIP vs mask.
- 5.2.2 Peak inspiratory airway pressure achieved with TTIP vs. mask ventilation

5.2.3 Dynamic airway resistance is defined as the peak inspiratory flow divided by the corresponding airway pressure.

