When apnea is observed, the subjects will be ventilated with one of the two ventilation techniques in a randomized crossover manner. Ventilation will begin either with TTIP followed by mask ventilation (Group A) or with the reverse sequence, that is, mask ventilation followed by TTIP (Group B), as shown in Fig. 5. After induction, ventilation will be obtained with the ventilator set to pressure-control mode at a rate of 10 bpm, inspiratory-to-expiratory time ratio (I:E) of 1:2, peak inspiratory pressure (PIP) of 20 cm H2O, and no PEEP. Subjects will start with one technique (Step 1) and cross over to the other technique (Step 2), as shown in **Fig. 5**. The subjects in Group A will first be ventilated with the TTIP technique. If the subjects are adequately ventilated, as defined by carbon dioxide measured during exhalation in at least one of the first three consecutive breaths, ventilation will continue until completion of 10 breaths, for 1 min (Step 1). Subjects will then be ventilated with mask ventilation (Step 2). In Step 1, if

ventilation fails with the TTIP technique for all of the first three consecutive breaths, the subject will be crossed over to the mask ventilation (Step 2). If ventilation fails again with all the first three consecutive breaths after crossover, the study will be terminated. The routine care is resumed including tracheal intubation or LMA insertion. Once Step 2 is completed, routine care will be applied, including oral or nasal airway placement or placement of a laryngeal mask airway. If tracheal intubation was planned, either rocuronium or succinylcholine will be given to facilitate muscle relaxation followed by subsequent intubation. Subjects in Group B will follow the same protocol as that in Group A, with the exception that the sequence of applying the two ventilation techniques will be reversed, as shown in **Fig. 5**.

[figure not shown]

Figure 5: The algorithm of the study procedure. The numbers listed on the chart represent the number of breaths. At each Step, 10 breaths were targeted. NO= ventilation was not effective as assessed clinically; YES= ventilation was effective as assessed clinically.

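### Outcome 5.2.3 is called airway resistance, but its flow term includes gas lost through the seal, so it cannot describe the airway unless leak is reported beside it

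*Combined protocol and SAP*

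**What the plan says.** Section 5 lists the ratio as secondary outcome 5.2.3: "Dynamic airway resistance is defined as the peak inspiratory flow divided by the corresponding airway pressure".

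The signals come from the machine. Section 7 preserves "All ventilatory settings and measured parameters displayed on the operating room ventilator", and the list that follows includes "flow waveforms, end-tidal carbon dioxide partial pressure, exhaled carbon dioxide waveforms". The sensor site is not given. Section 6 has the "ventilator set to pressure-control mode at a rate of 10 bpm", with "peak inspiratory pressure (PIP) of 20 cm H 2 O, and no PEEP".

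Section 1 expects leak with both techniques. For the mask: "Failure of mask ventilation often occurs due to leaks around the mask from an inadequate seal". For TTIP: "Since the cuff is not placed in the lumen of the trachea and is not inflated, the seal must be achieved via the lips", followed by "Even if a complete seal is not achieved, holding the lips around the tube can create a seal sufficient for positive pressure ventilation".

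The plan contains no leak measurement, no leak correction and no comparison of inspired with expired volume. The Section 7 rule on which breaths to use (five, or three after failure) names only expired tidal volume and peak inspiratory pressure. Section 7 sets out no analysis of 5.2.3 and does not say whether failed steps contribute to it.

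**The concern.** In pressure control the ventilator supplies the flow needed to hold the set pressure. Any flow signal on the machine side of the mask or lips is then the flow entering the patient plus the flow escaping at the seal. Dividing that sum by pressure gives a property of the whole system, whereas the outcome's name attributes it to the airway.

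The seal is made differently in the two techniques, so the leak contribution can differ between them, and the within-patient comparison does not cancel it. An analyst who follows the definition exactly could report a difference in airway resistance that is partly or wholly a difference in seal. A step with an obstructed airway and a leaking seal would not be recognisable from this outcome. Section 8 expects measured parameters, flow waveforms among them, to improve with TTIP, so a flow-based result may well be given weight.

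The name adds a second difficulty. Resistance is pressure over flow, whereas 5.2.3 is flow over pressure, which is a conductance. The direction in which leak misleads therefore depends on whether the reader follows the formula or the label.

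**Working it through.** The plan gives no figure for this outcome, so there is none to reproduce. The check uses a simple model of two parallel paths.

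**Inputs from the documents:** pressure control with P = 20 cmH2O and no PEEP (Section 6); flow as displayed on the ventilator (Section 7); leak possible at the mask and at the lips (Section 1).

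**Assumed, because the documents give no values:** airway resistance R of 10 or 40 cmH2O/L/s, or complete obstruction; leak conductance G from 0 to 0.10 L/s/cmH2O; alveolar pressure near zero at peak flow; no flow taken up by gas compression in the circuit.

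**Formulas**

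- Flow to the lungs = P/R
- Flow through the leak = P × G
- Outcome 5.2.3 = (P/R + P × G)/P = 1/R + G

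Example: P = 20, R = 10, G = 0.05. Flow = 20/10 + 20 × 0.05 = 2.0 + 1.0 = 3.0 L/s, and 3.0/20 = 0.150. Pressure cancels in this linear model, so the result does not depend on the value of 20.

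**Results:** flow/pressure in L/s/cmH2O, with its inverse (apparent resistance, cmH2O/L/s) in brackets.

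| Airway resistance | G = 0 | G = 0.02 | G = 0.05 | G = 0.10 |
|---|---|---|---|---|
| 10 | 0.100 (10) | 0.120 (8.3) | 0.150 (6.7) | 0.200 (5.0) |
| 40 | 0.025 (40) | 0.045 (22) | 0.075 (13) | 0.125 (8.0) |
| Fully obstructed | 0 (no finite value) | 0.02 (50) | 0.05 (20) | 0.10 (10) |

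1. **Direction within a technique.** For a given airway the ratio rises with G in every row, whatever R is assumed.
2. **Obstructed airway.** With G = 0.10 it returns 0.10, the same as an airway of resistance 10 with a perfect seal.
3. **Between techniques.** The difference in the outcome is (1/R_TTIP − 1/R_mask) + (G_TTIP − G_mask), and its sign depends on both terms. Take one technique with R = 10 and no leak (0.100) and another with R = 40. If the second leaks at G = 0.05 it scores 0.075 and the ranking by airway is kept. At G = 0.10 it scores 0.125 and the ranking reverses. The switch is at G = 0.100 − 0.025 = 0.075. The documents do not place the trial on either side of such a point.
4. **Relaxing the assumptions.** If alveolar pressure P_alv is above zero at peak flow, the airway term becomes (1 − P_alv/P)/R. Circuit compression adds a further flow term. Under TTIP the tube adds its own resistance to R. These change the airway part or add to the total, but none removes G.

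**The case against.** The best defence has four parts.

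- **Direction.** A reader might infer that the leakier technique will look better, or that the outcome is tilted towards TTIP. The documents support neither. Taken at its label, a higher ratio is a higher resistance and looks worse. The leakier technique also scores higher only if its excess leak outweighs any opposing difference in airway conductance, and the tube's own resistance under TTIP works against its leak. Section 1 moreover attributes most failed ventilation to obstruction by redundant tissue, so seal cannot be assumed to be the main difference between techniques. This part stands.
- **Size.** Every resistance and leak above is assumed, the sensor site is unstated, and the exact sum 1/R + G needs the listed assumptions. This stands too: the table shows the mechanism and does not estimate the bias in this trial.
- **Reach.** The plan draws no patency conclusion from 5.2.3 and specifies no analysis of it. The primary outcome rests on expired CO2 and outcome 5.2.1 on expired volume, neither of which is inflated by inspiratory leak, so a conflict with 5.2.3 could be noticed. This limits the harm. It does not make the ratio an airway measure, because a reader who sees the conflict still could not tell leak from airway without leak data.
- **Remedy.** One might conclude that 5.2.3 should be replaced by a version based on expiratory flow. The case for that is not clear. Gas can also escape through the seal during expiration, which biases that version downward, and end-inspiratory circuit pressure may not equal alveolar pressure when the airway is obstructed.

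What survives is the core: the flow used includes leak, leak is expected with both techniques, and nothing in the plan separates it out.

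**Conclusion.** The concern holds in a limited form. As defined, 5.2.3 is a flow/pressure ratio of the whole system. Leak raises it for any given airway, and an obstructed but leaking step can give a non-zero value. This rests on the flow being measured upstream of the mask or lips, which is the natural reading of a ventilator display but is not stated.

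The size of the bias and the technique it favours cannot be determined from the documents. Under the assumed leaks of 0.02 to 0.10 L/s/cmH2O, the ratio rises by a factor of 1.2 to 2.0 when airway resistance is 10 (0.120/0.100 to 0.200/0.100), and by 1.8 to 5.0 when it is 40 (0.045/0.025 to 0.125/0.025).

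A reader might take this as casting doubt on the trial's main result. It does not: the primary outcome and the sample size do not use 5.2.3.

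**What to change.** 1. Rename 5.2.3 a system flow/pressure ratio that includes leak. This also corrects the inverted use of the word resistance. State where flow and pressure are sensed.
2. Report leak fraction by technique from the recorded flow waveforms: (inspired volume − expired volume)/inspired volume. It covers leak over the whole breath. It would help separate the two cases that both score 0.10 above: close to 1 for the obstructed, leaking step (apart from gas compressed in the circuit) and close to 0 for the open, sealed one.
3. State which breaths enter 5.2.3 and whether failed steps are included.
4. Draw no conclusion about airway patency or airway resistance from 5.2.3 without the leak comparison beside it.
5. Optionally, add an expiratory-flow version as a sensitivity analysis, noting that leak during expiration biases it downward.

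The cost is a little more waveform analysis and a weaker claim for one secondary outcome. The signals are already to be recorded, so no new patients, equipment or procedures are needed.
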